5.2 Secondary endpoints

Participation rate to the breast cancer screening programme will be assessed as a percentage of women who participate, both in intervention and in the control group. The statistical hypothesis for the secondary endpoint is of non-inferiority. This hypothesis will be considered only if the null hypothesis related to the primary endpoint will be rejected.

Satisfaction with the information given (intervention and control group) will be measured using 8 items regarding length, quantity, clarity, balance, helpfulness in making decision and women willingness to recommend it to other women with three points scale.

The time spent on the pages in the web decision aid and in the web brochure will be assessed through Pickwick software. Only for the web decision aid, through the same software, the number of pages visited, the frequency of access and level of detail reached will be calculated.

Use of/experience with other screenings will be measured using one item on the participating in other screenings programme.

Decisional conflict will be assessed using the validated and widely used Decisional Conflict Scale-SURE version (28). This four-item scale will assess the women's knowledge of the options available, the clarity about the benefits and risks most important for them, sufficient level of support and being sure about the best choice. Since no Italian translation of this scale is available, the scale will be translated for this study.

The perceived risk of breast cancer will be assessed using one item with a five verbal response categories ranging from "much lower" to "much higher" than the average.

Internet use will be measured using one item regarding the frequency of the Internet use for health information.

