9.1.3 Sample size

The primary analysis will compare the proportion of women who make an informed choice, using the chi-squared test in the two study groups. Based on the previous studies (21, 22) we judge an absolute difference of 10% as the minimum important difference for the sample size calculation. Assuming that one of the group proportions is 50%, in order to achieve 80% power to detect a group difference with a two-sided significance level of 5%, we require 816 women at follow-up. Allowing for an estimated response rate of 15% and early drop-out of one-third of initial participants, we will invite 8160 women to take part in the study.

If the null hypothesis related to the primary endpoint will be rejected, the first of the secondary endpoints will be analysed. The power of the analysis for this non-inferiority test - with one-sided tail - will be considered according with the participation rate at breast cancer screening, as reported in the table below.

Participation rate at breast cancer screening (control group)	Participation rate at breast cancer screening (intervention group)	Δ	Number of patients for each arm	Power (1-β)
40%	35%	5%	408	0.29122
40%	30%	10%	408	0.82777
40%	25%	15%	408	0.99289
40%	20%	20%	408	0.99996

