9.2 Statistical analysis

We will conduct a descriptive analyses to describe the study participants. Possible baseline differences between trial arms will be statistically tested.

For primary endpoint statistical analysis will be performed on an intention to treat approach: all the randomised women compliant to follow-up will be included in the analysis in the groups assigned at the randomization. The impact of the web decision aid on the primary endpoint will be analysed using Chi-square test.

For secondary endpoints we will use Chi-square test to analyse binary endpoints and 2-sided t-test for continuous endpoints, with a significance level of 5%.

We will use SAS statistical software, version 9.2.

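### Participation is declared a one-sided non-inferiority endpoint, but section 9.2 assigns it a chi-square test, and no margin, one-sided alpha or success criterion is stated

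*Combined protocol and SAP*

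**What the plan says.** Section 5.2 says of participation: "The statistical hypothesis for the secondary endpoint is of non-inferiority". It adds the gate: "This hypothesis will be considered only if the null hypothesis related to the primary endpoint will be rejected". Section 9.1.3 repeats the gate and calls the analysis "this non-inferiority test - with one-sided tail". It then gives a power table with control participation of 40%, intervention participation of 35, 30, 25 and 20%, Δ of 5, 10, 15 and 20%, 408 women per arm, and power of 0.29122, 0.82777, 0.99289 and 0.99996. The text does not say whether Δ is a margin or an assumed true difference, which row applies, or what alpha was used.

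Section 9.2, which governs the analysis, says: "For secondary endpoints we will use Chi-square test to analyse binary endpoints". Continuous endpoints get a two-sided t-test, and the sentence ends with a 5% significance level. Participation is binary and is not exempted. The 10-point difference in sections 5.1 and 9.1.3 is the minimum important difference for informed choice. It is not a margin for participation.

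**The concern.** An analyst who follows section 9.2 would run a test of no difference. A non-significant result would not show non-inferiority, and a significant fall would not rule it out for a wide margin. An analyst who follows sections 5.2 and 9.1.3 would need a margin, an alpha and a success criterion, and would find none. The plan fixes when the test is done but not what counts as passing it.

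Participation is the only secondary endpoint with its own hypothesis, gate and power table. Whether a decision aid lowers screening uptake is a question readers will ask of this trial. With margin and alpha open, the same data can be reported as non-inferior or not, and nothing in the plan prevents that choice from being made after the results are known.

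**Working it through.** **Inputs.** From the section 9.1.3 table: n = 408 per arm, control rate 0.40, Δ = 0.05, 0.10, 0.15, 0.20. From section 9.2: a 5% level.

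**1. Reproducing the table.** Take Δ as the margin, true rates of 40% in both arms, the null variance at the rates in the first two columns, and a continuity correction of 1/n. (The primary sample size also needs a continuity correction: 408 per arm with it, 388 without.)

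Power = Φ[(Δ − 1/n − z·SE0) / SE1], with SE1 = √(2 × 0.4 × 0.6/408) = 0.03430 and SE0 = √{[0.4 × 0.6 + (0.4 − Δ)(0.6 + Δ)]/408}.

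For Δ = 0.10 and z = 1.96: SE0 = √(0.45/408) = 0.03321, and (0.10 − 0.00245 − 0.06509)/0.03430 = 0.946, so power is 0.828.

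| Δ | Stated | Margin, one-sided 2.5% | Margin, one-sided 5% | Difference test on listed rates, one-sided 2.5% |
|---|---|---|---|---|
| 5 | 0.29122 | 0.2918 | 0.406 | 0.288 |
| 10 | 0.82777 | 0.8280 | 0.895 | 0.833 |
| 15 | 0.99289 | 0.9929 | 0.997 | 0.995 |
| 20 | 0.99996 | 0.99996 | 0.99999 | 0.99999 |

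The last column is also continuity-corrected. The margin reading fits best and the difference reading is not far off. Both fit only at 2.5%. One-sided 5% overshoots the first two rows by about 11 and 7 points. Without the continuity correction, and with SE1 used throughout, the margin reading gives 0.308, 0.830, 0.992 and 0.99995 at 2.5%, and 0.426 and 0.898 in the first two rows at 5%, so the conclusion about alpha does not depend on that detail.

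**2. What one set of data would show.** Unpooled Wald limits for intervention minus control, 408 per arm, control 40%.

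- Observed 36%: SE = √[(0.36 × 0.64 + 0.24)/408] = 0.03395. The lower limit is −4 − 1.96 × 3.395 = −10.7 points, or −4 − 1.645 × 3.395 = −9.6 points. Chi-square p = 0.24. At a 10-point margin, alpha alone decides.
- Observed 33%: SE = 0.03362, 95% CI −13.6 to −0.4, chi-square p = 0.038. This is a significant fall that is non-inferior at 15 and 20 points but not at 5 or 10. With whole women (163 v 135), p = 0.042 and the lower limit is −13.5.
- Equal rates (163 v 163): p = 1.0, lower 97.5% limit −6.7. This is non-inferior at 10 points but not at 5.

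**3. Lowest intervention rate that passes** with 40% observed in control and a 95% CI: 41.7%, 36.7%, 31.6% and 26.4% at margins of 5, 10, 15 and 20 points. At 5 points the intervention arm must be observed above control.

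**4. Probability of declaring non-inferiority when the truth is 40% v 30%**, one-sided 2.5%: Φ[(M − 0.10)/0.03321 − 1.96], which is 0.025 at M = 0.10, 0.325 at 0.15 and 0.853 at 0.20.

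**5. Dependence on who is analysed.** Section 9.1.3 implies about 8160 × 0.15 = 1,224 randomised women, or 612 per arm. If all were analysed for participation, power at one-sided 2.5% with equal 40% rates and no continuity correction would be 0.43 at 5 points and 0.95 at 10, against 0.31 and 0.83 at 408 per arm by the same formula.

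**The case against.** The case for leaving this alone, or for ranking it lower, has four parts.

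- Section 9.2 is a single general sentence, and the specific text in sections 5.2 and 9.1.3 could be read as overriding it. That softens the conflict, but the specific text has no margin, alpha or success criterion, so it cannot be carried out either.
- If the 5% in section 9.2 is read as two-sided, its usual one-sided counterpart is 2.5%, which agrees with the table. This is the most natural way to reconcile them. It remains an inference by back-calculation, and nothing in the text says so.
- A significant fall that is still non-inferior can occur under any properly prespecified 15-point margin. That is true, and that example alone does not show harm. It shows that the chi-square result and the non-inferiority question have different answers. The harm comes from having four candidate margins and no choice among them.
- The endpoint is secondary and gated, so the primary test and its sample size are untouched. That is also correct. But the plan itself makes this a formal gated test, and a formal test needs a complete rule.

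**Conclusion.** The concern holds. Sections 5.2 and 9.1.3 call for a one-sided non-inferiority test. Section 9.2 prescribes a test that cannot deliver it, and no section supplies the margin, the one-sided alpha or the success criterion. Depending on which of the four Δ values is taken as the margin, power runs from 0.29 to above 0.999, and the chance of passing after a true 10-point fall runs from 2.5% at a 10-point margin to 85% at 20. These figures assume 408 women per arm and 40% control participation, both from the plan's table, with normal approximations. The one-sided 2.5% is inferred from the table's figures. The table does not settle beyond doubt whether Δ is a margin or a true difference, though the margin reading fits best. This must be fixed before the data are seen.

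**What to change.** In section 9.2, exclude participation from the chi-square sentence and add, for example:

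> Participation will be analysed as the risk difference (intervention minus control) with its confidence interval, only if the primary null hypothesis is rejected. Non-inferiority is claimed only if the lower limit lies above minus [M] points.

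Then:

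- Fix one M before data are seen and justify it as the largest acceptable loss of participation, not by which row of the table has enough power.
- State the one-sided alpha. Reconcile it with the table, which implies 2.5% (a two-sided 95% interval), and with the 5% in section 9.2.
- Label the Δ column in section 9.1.3 as margin or as assumed difference.
- State the power at the chosen margin. The table's values (0.29 at 5 points, 0.83 at 10) apply if one-sided 2.5%, equal true rates of 40% and 408 per arm are kept. Otherwise recompute it.

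The cost is wording in the protocol and SAP, with no extra participants. The sponsor commits to one margin and may have to report low power for it. At 5 points, 80% power at one-sided 2.5% would need 1,507 women per arm: (1.960 + 0.842)² × 0.48/0.05².

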9.2.1 Interim analyses

No interim analyses are planned.

10. DATA MANAGEMENT

10.1 Source data

Source documents are where data is first recorded, and from which participants' CRF data are obtained. These include, but are not limited to, web platform records with the questionnaires.

On all trial-specific documents, other than the signed consent, the participant will be referred to by the trial participant number/code.

10.2 Access to on trial participant data and study e-CRFs

Direct access to data will be granted to authorised representatives from the Sponsor, host institution and the regulatory authorities to permit trial-related monitoring, audits and inspections.

Access to the study clinical data entry web platform will be granted to trial staff through a computer-based credential generation system in the following manner:

- Centre PIs: will be granted Centre data entry credentials to allow for electronic signature of SAE forms, completed CRFs and meta-data entries which require PI approval (i.e. protocol deviations).

10.3 Data recording

Data collection will be performed using electronic CRFs exclusively.

The data will be registered in a MySQL database, to which only the site administrators (Zadig) will have access. The site administrators will insert users, who enter through centre lists. The system will give users an unambiguous ID, with which the data of each individual platform user will be associated. These data includes navigation, decisions, and questions. In this form, the data will be sent in CSV format. The data, subjected to statistical analysis, will be made anonymous, and provided in CSV format to the Mario Negri Institute. In general, the system permits tracing users in an unambiguous mode.

11. ETHICAL AND REGULATORY REQUIREMENTS

11.1 Ethical conduct of the study

The study will be performed in accordance with the ethical principles that have their origin in the Declaration of Helsinki and are consistent with ICH/Good Clinical Practice, and applicable regulatory requirements Participant data protection.

11.2 Compliance with Laws and Regulations

This study will be conducted in compliance with the protocol, the ethical principles that have their origin in the Declaration of Helsinki (64th WMA General Assembly, Fortaleza, Brazil, October 2013), the International Conference on Harmonization consolidated Guideline E6 for Good Clinical Practice and applicable regulatory requirement(s) including the following:

- Legislative Decree 08-11- 2012, n. 189 (Conversione in legge, con modificazioni, del decreto-

legge 13 settembre 2012, n. 158, recante disposizioni urgenti per promuovere lo sviluppo del Paese mediante un più alto livello di tutela della salute);

- Decision AIFA 07-03-2011 (Modifica delle appendici 5 e 6 al decreto del Ministro della salute 21 Dicembre 2007 concernente i modelli e le documentazioni necessarie per inoltrare la richiesta di autorizzazione, all'Autorità Competente, per la comunicazione di emendamenti sostanziali e la dichiarazione di conclusione della sperimentazione clinica e per la richiesta di parere al Comitato Etico);
- Ministerial Decree 08-02-2013 (Criteri per la composizione e il funzionamento dei comitati etici);
- Ministerial Decree 12-05-2006 (Requisiti minimi per l'istituzione, l'organizzazione e il funzionamento dei Comitati Etici per le sperimentazioni cliniche dei medicinali);
- Ministerial Decree 21-12-2007 (Modalità di inoltro della richiesta di autorizzazione all'Autorità competente, per la comunicazione di emendamenti sostanziali e la dichiarazione di conclusione della sperimentazione clinica e per la richiesta di parere al comitato etico);
- Authorization n. 9/2014 (Autorizzazione generale al trattamento dei dati personali effettuato per scopi di ricerca scientifica);
- Legislative Decree 30-06-2003, n. 196 (Codice in materia di protezione dei dati personali).

11.3 Ethics and regulatory review

The coordinating Independent Ethics Committee (IEC) should approve the final study protocol and related study documents including the final version of the Informed Consent Form and any other written information and/or materials to be provided to the participants. The investigator will ensure the distribution of these documents to the centres' Ethics Committee.

11.4 Informed consent

Due to the nature of the study intervention, the informed consent should be signed online and the informed consent process should be documented in the electronic record. The date that informed consent is given must be recorded on the eCRF.

11.5 Confidentiality

The Sponsor maintains confidentiality standards by coding each participant enrolled in the study through assignment of a unique participant identification number.

11.6 Changes to the protocol and informed consent form

If there are any substantial changes to the study protocol, then these changes will be documented in a study protocol amendment and where required in a new version of the study protocol (Revised Clinical Study Protocol).

The amendment is to be approved by the relevant Ethics Committee before implementation.

11.7 Audits and inspections

Authorised representatives of a regulatory authority or Ethics Committee may perform audits or inspections at the study centres, including source data verification. The purpose of an audit or inspection is to systematically and independently examine all study-related activities and documents, to determine whether these activities were conducted, and data were recorded, analysed, and accurately reported according to the protocol, GCP, guidelines of the ICH, and any applicable regulatory requirements.

12. STUDY MANAGEMENT

12.1 Administrative Structure

This study is sponsored by the IRCCS, Istituto di Ricerche Farmacologiche Mario Negri. The Sponsor will provide data management support.

The study Sponsor will allocate qualified personnel to the present trial. All the figures involved in the study design, management and conduct are qualified according to Italian laws and regulations concerning clinical trials, and specifically trained on the objectives, procedures and instruments of this trial.

12.2 Publication of Data

Results derived from the trial are property of the Sponsor, which shares them with all participating investigators.

Every publication of the trial results will be written on the basis of the analyses performed by the Sponsor. Publications will be decided by the Sponsor. The name list at the end of each article will include all the other participants who contributed to study coordination and data analysis. Furthermore, all manuscripts will include an appropriate acknowledgment section.

Rules for abstract presentation will be the same as for extended papers.

12.3 Clinical Study Report

At the end of the study, clinical study report will be written and distributed to all centres.

12.4 Finances

The study is Sponsored by the IRCCS, Istituto di Ricerche Farmacologiche “Mario Negri” which plays the role of not-for-profit sponsor.

The AIRC-Italian Association for Cancer Research (Number IG2015-17274) supports the entire project study, providing also the economical support for the study.

12.5 Insurance

Not applicable.

12.6 Study timetable and end of study

The end of the study is defined as ‘the last follow-up questionnaire of the last participant undergoing the study’.

The study is expected to start in September 2017 and to end in December 2018.

14. APPENDIX

14.1 Appendix 2: Control group – Web brochure

Screening is a public health program where healthy population, at an age judged to be at risk, is invited by local health system to undergo free preventive examinations, such as mammography, Pap test or fecal occult blood test.

Screening may help anticipate cancer diagnosis and treatment, allowing less invasive surgical interventions. For breast cancer screening every woman, between 50 and 69 years of age, receives a letter of invitation with a fixed appointment to carry out a free mammography every 2 years. Scientific research has proven that screening for breast, uterus, and colorectal cancers can save many lives.

MAMMOGRAPHY

Currently, for women aged between 50 and 69, mammography is the most effective test to detect tumors that are not yet symptomatic and are not palpable.

It is a radiograph of the breast that uses very low X-ray doses.

To obtain a clear result it is necessary to compress the breasts. This compression can be bothersome or may cause slightly pain, but lasts a few seconds. The radiographer is highly qualified and the equipment used is technologically advanced and controlled. All this makes it possible to obtain images of excellent quality.

For greater security on the diagnosis, the images are examined separately by two radiologists to ensure greater accuracy. However, like all tests, it is not foolproof: in some cases, it may not recognize a tumor that is there or suspect a non-existent tumor.

WHY A MAMMOGRAPHY?

In Italy, breast cancer is the first cancer among women due to incidence, i.e. number of new cases of breast cancer in a year. It is the most common cancer among women, with tens of thousands new cases and 11,000 deaths. The mammography performed regularly allows an early diagnosis, before the onset of symptoms, and the possibility of intervening with a high probability of definitive recovery. Data support that, for every 1000 women aged between 50 and 69 years who regularly perform mammography, 7-9 lives are saved within 20 years.

WHAT ARE THE LIMITS OF THE MAMMOGRAPHY?

- In general, every 100 women who had a mammography, about 5 must repeat the exam or undergo in-depth examinations. For 4 of them it is actually a "false alarms", as the in-depth analyses exclude the presence of a tumor (the so-called false positives). The disadvantage is mainly represented by the anxiety that a woman can experience in such situation.
- Mammography is not always able to detect the tumor when it is present. In some cases the breast is very dense (i.e. it contains many glands) and this makes it difficult to detect the tumor (the so-

called false negatives).

- In some cases the disease develops very quickly in the interval between two screening tests (so-called interval cancers). Even if the mammography did not show anomalies, it is important to pay attention to breast changes such as hardening, skin deformation, leakage of fluid from the nipple and the presence of axillary nodules. If you note such anomalies, you should contact your doctor immediately.
- Some anomalies, among those detected by mammography, are not destined to become invasive tumors and to compromise the woman's health (the so-called overdiagnosis).

In these cases (1 case of cancer every 10 diagnosed) it is possible to have not necessary interventions. Unfortunately, this is inevitable as it is still not possible to distinguish from the beginning life-threatening tumors from the others.

WHAT CAN THE OUTCOME OF THE MAMMOGRAPHY BE?

- If nothing suspicious appears, you will receive a negative result letter.

It is important to know that the purpose of mammographic screening is to identify malignant tumors recognizable by x-rays; other breast diseases are not considered.

- If mammography shows doubtful images, you will be contacted and invited to go to the screening center to carry out in-depth examinations, which can include other mammography, echography or a collection of a small sample of breast tissue (biopsy). Most of these doubt cases are not due to the presence of a tumor, nevertheless it is necessary to perform these additional exams to be sure.

14.2 Appendix 1: Intervention group – Web decision aid. Content of decision aid.

Home-page

Dear Miss, thank you for having agreed to help us.

In a few weeks, you will receive an invitation to take part in an organized mammography screening program. According to the Italian Ministry of Health recommendations, based on scientific studies, the use of this test in the screening program can reduce mortality due to breast cancer among women of your age.

Obviously, the decision to participate or not is entirely up to you.

Here you will find some up-to-date information about mammography screening, its pros and cons, including the controversies and different opinions of experts.

We know that your choice will not be based only on this information but other aspects too will affect the decision: your life experience, your perception of the risk of developing this disease and your own values. These are very important aspects that drive many of our choices: they shall therefore recall at the end of the navigation when you make your final decision.

Before taking a decision, explore these pages, in your own time: the icon at the top “Where I am” will help you navigate. When you feel you know enough, just click on “Ready to choose” at the bottom of the page.

What is mammography screening?

Mammography is a radiological breast examination that uses very low X-ray doses.

Mammography can identify lesions or nodes you cannot yet feel. This is why it is used for screening in women who have no symptoms or signs, so as to detect any breast cancers at an early stage.

It is advisable to take part in an organized mammography screening program because it is reliable, with quality control and a standard care schedule already sets up in case further examinations are required. Outside organized mammography screening programs there is no regular quality control by third parties, so quality is not guaranteed.

The mammography screening and any subsequent diagnosis and treatment (if necessary) within the organized mammography screening program are free of charge.

The pros and cons of mammography screening

Mammography screening can provide both benefits and harms, like any other medical examination.

Mammography does not prevent breast cancer but it helps find tumors in an early stage when there is less invasive and more effective treatment.

The main advantage is the reduction of mortality due to breast cancer for women who participate in the organized screening program.

The principal disadvantage is harder to grasp. Sometimes there is unnecessary and useless treatment (overtreatment), and if it is useless it is harmful, of tumors discovered by the screening that would resolve themselves spontaneously during the woman's life (overdiagnosis). These malignancies look just like other tumors but either do not grow or grow very slowly. Unfortunately, so far there is no way to distinguish whether a tumor is actually not harmful, so all cases are treated and the woman will not know what her situation was.

[figure not shown]
It is only possible to estimate the reduction of mortality due to breast cancer by the mammography screening program, and of extra tumor diagnosis (overdiagnosis).

Participation in the screening provides the following benefits and harms to be assessed before taking a decision:

- Reduction of mortality due to breast cancer
- Overdiagnosis
- Less invasive treatments
- False positives or false negatives
- Radiation damage
- Inconvenience of the examination

What happens in the next 30 years?

What happens at 1000 women aged 50 in the next 30 years

Out of 1000 women aged 50 who regularly participate in a mammography screening program, in

the next 30 years:

- 71 will receive a diagnosis of breast cancer (discovered by screening or from clinical symptoms)
- 12 will die from breast cancer
- 8 will not die from breast cancer thanks to the screening
- 4 will receive overdiagnosis and useless treatments

If the same 1000 women are followed without a mammography screening program:

- 67 will receive a diagnosis of breast cancer
- 20 of them will die due to the breast cancer

In other words, in the next 30 years:

Some women will die from breast cancer anyway: 12 of the 1000 who participate in the mammography screening program compared to 20 if the screening program did not exist. Therefore 8 out of 1000 women are saved from death due to breast cancer; 4 of the 1000 women receive a diagnosis and are then treated uselessly for tumors detected by the screening that would probably never emerge. If there is no mammography screening program, there is no overdiagnosis and only evident tumors are treated.

At what age is mammography screening recommended?

In Italy the mammography screening program is carried out every two years for women aged 50-69 because there is impressive evidence of the reduction of mortality.

In some Italian regions (Emilia Romagna, Piedmont and Tuscany), the mammography screening program is extended to women aged from 45 to 49 every year and between 70 and 74 every two years. For these age bands the demonstration of the utility of screening is considered sufficient, though the balance of the related benefits and harms is still debated.

The European Code against Cancer (2015) confirmed the recommendation for women aged 50-69 to do the organized mammography screening and, in certain circumstances, also women aged 45-49 and 70-74.

The risks related to radiation

Mammography uses X-rays, namely high-energy radiation (also called ionizing) that may damage cells that absorb it, including the development of tumors. Mammography based on quality criteria employs low doses of X-rays so the risk of tumors developing is practically zero.

The amount of radiation from a mammography is comparable to that absorbed in a few weeks from “background radiation”, meaning from radioactive substances in the ground and buildings and to which everyone is normally exposed.

Mammography is comparable to a chest X-ray and is much less dangerous than an abdominal tomography scan.

Comparison of doses of radiation from different examinations in adults

Method	Effective dose in adults*	Time needed to absorb the same dose from background radiation
Computerized Bone Mineralometry	0.001 mSv	3 hours
Limb X-ray	0.001 mSv	3 hours
Intraoral X-ray	0.005 mSv	1 day
Chest X-ray	0.1 mSv	10 days
Mammography	0.4 mSv	7 weeks
Spinal X-ray	1.5 mSv	6 months
Upper abdomen X-ray	6 mSv	2 years
Chest computed axial tomography (CAT scan)	7 mSv	More than 2 years
Lower abdomen X-ray	8 mSv	About 3 years
Abdomen-pelvi CAT scan	10 mSv	More than 3 years

* The effective dose used for the comparison is quantified considering the type of radiation and the specific sensitivity of the body part involved; the measurement units are milliSievert (mSv).

Organized mammography screening program, a quality program

In the organized mammography screening program, all women of your age are regularly invited for a free mammography at a clinical center involved in the program that guarantees full assistance, for diagnosis and treatment of any breast cancer.

The quality of all Italian organized mammography screening programs, including the one you are invited to, is monitored and evaluated within national and international initiatives (see the sources above and on the right). Outside this program there is no way of judging, as there is no regular data collection.

At your appointment, a radiographer will take two X-rays for each breast from different angles. The breast is pressed between two plastic plates and this may cause slight discomfort. However, the stronger compression the less radiation you will receive and the more accurate will be the exam.

The X-rays are then assessed by two expert medical radiologists who read at least 5000 exams a year as a quality standard.

If all is well, you will receive a letter or an e-mail. If there is any doubt you will be contacted by phone.

What result will the mammography give?

[figure not shown]
For most women, the result is normal, meaning nothing has been found (negative result). A negative result is reassuring but it does not mean no tumor will ever develop.

Rarely, the tumor can escape observation, (called “false negatives”), for example in hard-to-interpret cases, namely if the breast is dense, or it might develop between this screening mammography and the next invitation: these are referred to as “interval tumors”. Therefore, talk to your doctor if you notice any changes in your breast between two exams, such as nodules you can feel, skin deformation or hardening, or a bleeding or retracting nipple.

A doubtful result or “positive mammography” means the radiologist has seen images like nodules, masses, calcifications or others that could signal a tumor and thus call for more investigation. This may cause you anxiety and concern but it does not imply a malignant disease. If the suspicion is not confirmed by further tests it is called a “false positive”.

What happens at each screening?

What happens at women within the mammography screening program?

Data from the Italian organized mammography screening program

In Italy, out of 1000 women participating in each screening, on average:

- 950 women will receive a “negative” result (no tumor) after the first examination and will be invited to attend the next examination; for 1-2 of them it will prove to be a “false negative”;
- 50 women of the 1000 will receive a “positive” result (suspicion of tumor) and a further appointment will be set for deeper analysis.

Among these 50 women:

- for 45 of them, the suspicion of a tumor will prove unfounded (false positive) and they will be invited to attend the next screening;
- for the other 5 the suspicion will be confirmed and they will be treated in qualified centers.

In other words:

- In the majority of cases the mammography is normal (negative results for 950 out of 1000 women);
- Many doubtful cases prove normal after further analysis (false positive for 45 out of 50 women);
- There is the extremely rare possibility that a tumor is not identified (false negative). This may happen to 1-2 women out of 1000 and the tumor is generally discovered because of a nodule or breast lesion.

To discover what you can expect 30 years after taking part in a screening program, [click here](#).

Diagnostic programs in uncertain cases

When the first mammography gives a doubtful result, the woman is invited for a breast examination and a second mammography and/or echography (both not invasive) to confirm or exclude the real presence of a tumor.

The breast examination is done by a skilled physician who will recognize visually and by palpation even small but significant breast changes.

When it is not possible to exclude a tumor even after further examinations, sampling the suspect nodule is generally suggested (biopsy or fine-needle aspiration): this occurs in about 30% of cases. The result of the biopsy is communicated by the physician who first visited the patient, at her next appointment.

Breast density

The breast comprises a glandular part and an adipose one (fat). When the adipose part is the main one the mammography profile is clear, while the appearance is denser when the glandular component is greater.

When the breast is dense the mammography is harder to interpret and a very small tumor may not be detected giving a “false negative” result.

Usually the density changes over time as the glandular part decreases with age. That explains why in general mammography is clearer in older women.

What is breast cancer and how can it be treated?

The risk of breast cancer depends on different factors (such as age, family history and life-style) and it is the female tumor that causes the most deaths (see chart 1 *I numeri del cancro in Italia. Rapporto AIOM AIRTUM, 2016*). Nowadays, there is every chance of a cure (see chart 2 *I numeri del cancro in Italia. Rapporto AIOM AIRTUM, 2016*) through the risk of recurrence remains for many years. The probability of a cure depends on the tumor’s biological features.

A tumor can appear in several forms and is caused by uncontrolled growth of breast cells that become malignant.

The tumor cells can grow (when inside the mammary gland this is defined as an *in situ tumor*) and migrate to other organs, in the form of metastasis. A metastatic tumor is harder to fight so prompt intervention is always important.

If the tumor is diagnosed at an early stage, usually treatment is less aggressive.

For most women with breast cancer only the tumor is removed, surgically, with its surrounding tissue, or the whole breast, depending on the extent of local disease. Other treatments, in addition and in different sequences, include radiotherapy, chemotherapy or hormone therapy, which are useful to reduce the chances of the disease recurring. Further therapies are possible or are being tested, especially with biologic drugs for specific groups of patients.

The main risk and protective factors

The risk of breast cancer depends on several factors that can be divided into two groups: those that are unchangeable and those that can be reduced by adopting a correct life-style.

Age: the risk rises with age and more than 75% of breast cancers are in women over 50.

Family history: some families report several cases of breast cancer among first-degree (mother-daughter) or second-degree relations (sisters).

Genes: BRCA1 and BRCA2 genetic mutations are responsible for almost half of hereditary breast cancers (5-7% of the total).

Age, family history and genetic patterns are factors to be considered in assessing one's own risk, though they cannot be changed. In addition, other factors can influence the risk of breast cancer, raising or lowering it. For example, a high level of estrogen - the main female hormone - facilitates breast cancer. Any other factors that boost their expression, such as hormone replacement therapy (HRT) increase the risks. Pregnancies lower estrogens production, with a protective effect.

In general, a healthy life-style with a diet rich in fruit and vegetables (unrefined cereals, legumes, non-starchy vegetables, and fruit), less alcohol (no or only one glass of wine a day), weight control, especially after the menopause, can all be protective against breast cancer.

To reduce the probability of breast cancer

What to do	What not to do
Keep ideal weight (BMI <24,9 kg/m²) with a diet based on vegetables (unrefined cereals, legumes, starchy vegetables, and fruits), no alcohol or 1 glass of wine a day at the most	Marked overweight (BMI>28) in menopause
Follow the Mediterranean diet with a supplement of extra-virgin olive oil	Suffer of metabolic syndrome after menopause
Eat fruit and vegetable during adolescence (≥ 3 portions a day)	Drink more than a single dose of alcohol a day (most risk during adolescence)

What to do	What not to do
